7. EVALUATIONS AND VISITATION SCHEDULE

Participants will preferably be evaluated by the same evaluator at the beginning of the study (screening and randomization: D-1 and D0 respectively).

During follow-up, including the assessment of participants who were not discharged after the end of treatment (D21) and at two visits after discharge: two weeks (D28) and sixty days (D60) after the end of treatment.

Table 39 shows the tests to be used to assess eligibility criteria and to monitor safety and efficacy during the study period.

The coronavirus viral load will be detected every 2 days. The treatment will

last a maximum of 14 days, and can be stopped early if two consecutive negative RT-PCR tests are obtained, or if the participant decides not to continue in the study.

During the course of treatment, if the results of safety and efficacy testing show changes of concern, the investigators must determine whether or not the participant should continue with treatment. The Principal Investigator may adjust the procedures performed during the hospital stay according to the research participant's condition and the results of clinical examinations. The schedule of study procedures and examinations is detailed in Table 9.

ltem	Requirements and outcome measures
Demographic Information	Nationality, age, sex, height and weight
Anamnesis	Past/current medical history (history of illness, history of operation), history of anaphylaxis, medication use, alcohol use, drug abuse, participation in clinical trials, surgical treatment, or pregnancy/lactation.
Vital signs	Body temperature, heart rate, respiration, blood pressure
DIGITAL OXIMETRY	-
Blood glucose	Blood glucose level
Detection of viral load by RT- PCR	Sample of airway epithelium
ECG	12-lead or 18-lead ECG
CT of the lung	-
CBC	RBC, Hb, HCT, MCV, MCH, MCHC, WBC, NEUT #, LYMPH #, MONO #, EOS #, BASO #, PLT
Biochemical Examinations	AST, ALP, Cholinesterases, ALT, Alb, TP, TBIL, DBIL, GGT, Creatinine, UREA, UA, K ⁺ , Na ⁺ , Cl ⁻ , Lactate, Ca ⁺ , P.
Taxa de sedimentação de eritrócitos (ESR)	ESR
C-reactive protein (CRP)	-

Cardiac markers and enzymes	Troponin I, BNP, CK, CK-MB
Septicemia	РСТ
Blood Lactic Acid	Lactic Acid
Interleukin-6	IL-6
Coagulation test	TP, TTPA, FIB, TT
Immunological markers	IgA, IgG, IgM, complement C3 and C4
Infectious Diseases	Ab Hepatitis A, Ag Hepatitis B, Ab Hepatitis C, Ab HIV, AbTreponema pallidum
Respiratory parasites	Legionella pneumophila, Mycoplasma pneumoniae, Coxiella burnetii (Q-Rickettsia), Chlamydia pneumoniae, adenoviruses, respiratory syncytial virus, influenza A virus, influenza B virus, Parainfluenza virus.
Triple rapid test for respiratory parasites	Respiratory syncytial virus, adenovirus, Mycoplasma pneumoniae
T-lymphocyte subsets	CD4+ and CD8+ T-cell count
Pregnancy Test	Applicable to female participants

Table 9: Parameters for safety and efficacy evaluation

7.1. ASSESSMENT OF EFFECTIVENESS

7.1.1. Primary Efficacy Evaluation (Objective)

- Proportion of participants with clinical status improvement [Period: until D15, approximately 14 days].
 - The criterion for a participant to have an improvement in clinical status is a decrease on the WHO Clinical Improvement Ordinal Scale in at least one category compared to screening (WHO, Jun/2020).

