If hospitalization is indicated, a rapid test for COVID-19 will be performed, and if the result is positive, the clinical study will be presented by the prospecting team and an invitation to participate in the study will be extended. The consent process will be conducted by the prospecting agents in the field, duly delegated and trained to conduct the process, as well as to apply the Informed Consent Form (ICF). Multimedia resources will be used to clarify and instruct the volunteer about the objectives and details of the study. At the end of all the necessary clarifications, the volunteer will be asked to sign the ICF, where one copy will remain with the volunteer and another will be destined to the research center.

If the patient accepts to be a study volunteer, he/she and his/her companion, if applicable, will be informed of the study procedures, including the laboratory tests for the screening period, the criteria for inclusion and exclusion from the study, his/her rights and duties, the period of treatment and follow-up. The eligibility criteria may be

explored after the anamnesis, laboratory tests, and imaging tests have been performed, but may also be suspended at any time prior to complete evaluation if exclusions are identified by the study team. After this phase, the participant will be invited to sign the ICF and, only after signing, the volunteer will be included in the study. Clinical and laboratory evaluations and collection of nasopharyngeal and oropharyngeal swab specimens for RT-PCR testing confirm the eligibility of the study participant and will be assessed once all screening values are available.

Research participants who meet the inclusion criteria and do not meet the exclusion criteria, and who have eligibility assessed by the Principal Investigator, will be eligible.

The volunteer will then be transferred to Santa Casa de Misericórdia de Campos, via the regulatory center for hospital admission in a ward/apartment, and will be immediately randomized to follow the Treatment Protocol for COVID-19 of Santa Casa de Misericórdia de Campos (ANNEX1), as listed below:

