5.2.3. Inclusion Criteria

- Age ≥18 years, regardless of gender;
- Patients hospitalized in moderate to severe stages in line with the Ministry of Health classification⁹;
- Positive diagnostic test for SARS-CoV-2 by molecular amplification of the virus RT-PCR diagnosed from respiratory specimen (nasopharyngeal, oropharyngeal, lower respiratory tract [e.g., sputum) collected <96 hours before randomization;

⁹The Brazilian Ministry of Health classifies the symptoms of COVID-19 into:

Mild: Flu-like symptoms (cough, sore throat, or runny nose), followed or not by: anosmia (olfactory dysfunction), ageusia (taste dysfunction), runny nose, diarrhea, abdominal pain, fever, chills, myalgia, fatigue, headache;

Moderate: Persistent cough + daily persistent fever or persistent cough + progressive worsening of another symptom related to COVID-19 (adynamia, prostration, hyporexia, diarrhea) or at least one of the above symptoms + presence of risk factor.

Severe: Severe acute respiratory syndrome: influenza syndrome presenting with dyspnea/respiratory distress or persistent chest pressure or $_{02}$ saturation (SpO2) less than 95% on room air or Bluish coloration of lips or face.

- Time between symptom onset and inclusion ≤14 days;
- Hospitalization within 48 hours of study inclusion;
- Availability for follow-up during the study period;
- Voluntary adherence to participate in the study and signing of the Informed Consent Form.

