7.3. VISIT SCHEDULE

The research center is responsible for defining the strategies for recruitment and initial screening of research participants, knowing that the screening process can be suspended at any time if exclusions are identified by the study team.

VISIT 1: INTIAL (D-1)

Patients with moderate to severe symptoms for COVID-19, hospitalized or with indication for hospitalization, aged over 18 years, will be invited to participate in the study. If the volunteer accepts to be a participant, he (she) and his (her) companion, if applicable, will be informed of the study procedures, including laboratory tests in the screening period, the criteria for inclusion and exclusion from the study, as well as his (her) rights and duties. Only after signing the informed consent form, the patient will be included in the study and the eligibility criteria can be explored after the anamnesis, laboratory tests, nasopharyngeal and oropharyngeal swab specimen collection for RT-

PCR testing, and imaging tests. **Confirmation of study participant eligibility will** be assessed once all screening data are available.

The following procedures will be performed in visit V1:

- Invitation to volunteer;
- Consent process and signing of the TCLE;
- Verification of inclusion and exclusion criteria;
- Demographic data collection;
- Anamnesis;
- Collection of medical history data;
- Vital signs monitoring;
- Collect blood and respiratory samples (nasal and oropharyngeal swabs) for screening tests;

- Collecting blood for a pregnancy test (women of childbearing age).
- Eligibility assessment and confirmation with the Principal Investigator.

VISIT 2: RANDOMIZATION (D0)

. After confirmation of eligibility for the study by meeting the inclusion and exclusion criteria and performing the screening procedures, eligible individuals will be randomized to the experimental or control group and then transferred to Santa Casa de Misericórdia de Campos for hospitalization in a ward/apartment, and will follow the Treatment Protocol for COVID-19 - 2nd Version (July 02, 2020) of Santa Casa de Misericórdia de Campos.

The following procedures will be performed in visit V2:

- Validation of eligibility by the Principal Investigator;
- Randomization of research participants;
- Admission or transfer of the participant to the apartment or infirmary of Santa Casa de Misericórdia de Campos;
- Dispensing of the experimental drug;
- Accounting for the experimental drug.

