7.5. VIEWING WINDOW

To be eligible to participate in the study, among the proposed inclusion criteria is the presence of a positive diagnostic test for SARS-CoV-2 by molecular amplification of the virus in a respiratory sample (nasopharyngeal, oropharyngeal, lower respiratory tract, e.g.: sputum) collected <96 hours before randomization. For this reason, the time between screening and randomization should not exceed 4 days.

To attend the end-of-follow-up visits (**D28 and D60**) participants will have the possibility to **advance or delay by up to three days** from the initially scheduled date.

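### The primary endpoint is referred to a screening score that can predate hospital admission and the first dose, so some participants can be misclassified as improved or not improved

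*Protocol*

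**What the plan says.** Section 7.1.1 defines improvement as "a decrease on the WHO Clinical Improvement Ordinal Scale in at least one category compared to screening", assessed up to D15. The synopsis, Section 4 and the method table in Section 11.3 carry the same definition. No other baseline is named for this endpoint.

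On timing, Section 7.5 says that "the time between screening and randomization should not exceed 4 days", and Table 10 gives the D-1 visit a window of 4 days. Randomisation is D0. Treatment starts on D1, with dosing at 8 pm (Section 7.3).

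On care setting, the sections differ:
- Section 5.2.3 requires "Patients hospitalized in moderate to severe stages in line with the Ministry of Health classification", with a companion criterion that ties hospitalisation to within 48 hours of inclusion.
- Section 7.3, Visit 1, invites "Patients with moderate to severe symptoms for COVID-19, hospitalized or with indication for hospitalization, aged over 18 years".
- Section 5.2.1 states: "The consent process will be conducted by the prospecting agents in the field". Transfer to the study hospital follows the eligibility assessment, "via the regulatory center for hospital admission in a ward/apartment, and will be immediately randomized".
- Section 7.3, Visit 2, gives the opposite order: "eligible individuals will be randomized to the experimental or control group and then transferred to Santa Casa de Misericórdia de Campos for hospitalization".

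Table 4 places symptomatic outpatients at 2 or 3 and hospitalised, non-intubated patients at 4 to 6. Table 10 has no row for the WHO score at any visit. Its D0 column holds only randomisation, dispensing and drug accounting.

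**The concern.** A responder endpoint should measure change from the state in which treatment begins. Here the reference can be several days older than the first dose and can come from a different care setting. On this scale the step from 3 to 4 is admission itself, so a score can rise because the patient was moved to a bed. It can also fall before any study drug is given. As the threshold is a single category, one such step can be enough to change the classification.

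At stake is what the primary endpoint means (change on treatment, or change since first contact) and some dilution of the difference between arms. The protocol itself fixes the reference, so a later analysis plan that used a pre-dose baseline would contradict it.

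**Working it through.** **1. Gap from screening to first dose.** The nominal gap is D-1 to D1, with one day of it before randomisation. The maximum is 4 days to D0 (Section 7.5) plus D0 to D1, about 5 days.

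**2. Does the reference change the classification?** Two cases on Table 4:

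| Case | Screening | Just before first dose | D15 | Against screening | Against pre-dose |
|---|---|---|---|---|---|
| (a) screened before admission | 3 | 4 or 5 | 3, still symptomatic | not improved | improved |
| (b) falls one category before dosing | 5 | 4 | 4 | improved | not improved |

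The two references disagree only for courses of this kind. A participant who goes from 5 to 4 before dosing and later reaches 0–2 is improved on both. A participant screened at 3 who leaves hospital with no detectable virus and scores 0 is also improved on both.

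**3. The plan's sample size, reproduced.** Inputs from Section 11.1: p1 = 0.667, p2 = 0.281, difference 0.386, margin 0.205, alpha 0.05, beta 0.2, ratio 1:1.

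n = (z_α + z_β)² × [p1(1−p1) + p2(1−p2)] / (difference − margin)²

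= (1.645 + 0.842)² × (0.2221 + 0.2020) / 0.181² = 80.04, so 81 per group.

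With 10% dropout, 81/0.9 = 90 per group and 180 in total. This matches the protocol. It is reproduced with a one-sided 5% level, so the margin column below uses that level.

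**4. Effect of misclassification.** The documents give no affected share, so q is an assumption. Let a share q in each arm have its classification set by the pre-dose step. The rates become q + (1−q)p if these participants are all counted as improved, or (1−q)p if all are counted as not improved. Either way the difference is (1−q) × 38.6 points. Power with 81 per group, showing the range over the two versions:

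| q | Difference (points) | Against 20.5-point margin, one-sided 5% | No difference, two-sided 5% |
|---|---|---|---|
| 0 | 38.6 | 0.80 | >0.99 |
| 5% | 36.7 | 0.72 | >0.99 |
| 10% | 34.7 | 0.62 | >0.99 |
| 20% | 30.9 | 0.41–0.42 | 0.98–0.99 |
| 30% | 27.0 | 0.23 | 0.95–0.96 |

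The margin appears only in the sample-size call. Section 11.3 plans logistic regression on allocation group with two-sided tests and states no margin, so the last column is the one that matches the planned analysis.

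**The case against.** A reader might infer that participants are often screened before admission. The documents do not support that. The inclusion criteria require hospitalised patients and link hospitalisation to within 48 hours of inclusion, Visit 2 provides for admission or transfer, and some patients may come from another hospital. No frequency is given. What stands is that Sections 5.2.1 and 7.3 describe a route in which screening precedes admission, and that this does not fit the inclusion criterion as worded.

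The 4-day gap is a ceiling set by the RT-PCR window. The nominal gap is one day, RT-PCR results are planned every 24 hours, and Section 5.2.1 has immediate randomisation. That limits pre-dose change but does not remove it.

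It is also tempting to say that the participant in case (a) has recovered. Table 4 defines 3 as symptomatic and needing assistance, and two negative RT-PCR tests are among the discharge criteria. Case (a) is therefore a narrow group: participants who leave hospital still symptomatic, for example at the end of the 14 days.

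Finally, the HOPE-1 rates behind the sample size also used screening as the reference, so the endpoint matches its planning data. This is true. However, the HOPE-1 scores listed in Section 11.1 all lie between 0 and 2, so nobody there crossed the 3-to-4 boundary and those data say nothing about the admission step.

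**Conclusion.** The point holds. As written, the rule can count a participant as not improved who came down from the admission state, and can count one as improved with no change on treatment. The number affected is unknown and is confined to participants whose classification flips, not everyone whose score moves before dosing.

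For size, a 10% share in both arms would cut the planned difference from 38.6 to 34.7 points. Power against the 20.5-point margin would fall from 0.80 to about 0.62. For the planned two-sided comparison with no difference it would stay above 0.99, and at 30% it would still be at least 0.95. These figures rest on the protocol's planning rates, 81 evaluable participants per group, and an equal share in each arm. Randomisation and blinding make the pre-dose step similar between arms. Whether a participant then flips depends on the later course, so exact equality is an assumption.

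Two stronger readings are not supported. One is that the rule hides a true effect: at the planned rates the power loss is serious only against a margin that the planned analysis does not test. The other is that it favours one arm: allocation is 1:1 and double-blind, and the expected consequence is dilution.

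**What to change.** In the synopsis, Section 4, Section 7.1.1 and the matching row of the Section 11.3 table, replace the comparison with screening by a comparison with the last WHO score recorded after admission and before the first dose (D0, or D1 pre-dose). Add that score to Table 10. Because it allows a D1 pre-dose score, this reference can be obtained under either order of admission and randomisation.

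Separately, reconcile Sections 5.2.1, 5.2.3 and 7.3 on whether randomisation comes before or after admission, and on when the hospitalised criterion must be met.

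The cost is a protocol amendment, one extra dated score in the eCRF, and a small departure from the HOPE-1 planning definition. The sample size of 180 does not change. Section 7 already foresees evaluation at both D-1 and D0, and symptoms, vital signs and oximetry are already monitored daily from D1. If enrolment has begun, the pre-dose score of participants already included would have to be taken from source records by staff blind to allocation.

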7.1.2. Secondary Efficacy Evaluation (Endpoints)

- Proportion of participants with a clinical outcome of cure during the study; [Period: until D15, D21, and D28, approximately 14-30 days].
 - $_{\odot}$ The clinical endpoint of cure is defined in this protocol as the absence of viral RNA in collected samples and clinical conditions for hospital discharge¹⁴.
- Time to normalization of body temperature (below 37.6°C axillary); [Period: until D15, D21 and D28, approximately 14-30 days]
- Tempo de melhora da diarréia, mialgia, fadiga, mal-estar, tosse, dispnéia e cefaléia;
 [Período: até o D15, D21 e D28, aproximadamente 14-30 dias]
- Changes in liver and kidney function baselines, and inflammatory and immunological markers: [Period: until D15, D21 and D28, approximately 14-30 days]
 - Lab tests performed on days D1, D3, D5, D7, D9, D13, D15, D21, D28, and
 D60.
- Evaluation of the time to negative conversion of the SARS-CoV-2 viral load by RT-PCR between AZVUDINE (FNC) group and control group; [Period: until D15, D21 and D28, approximately 14-30 days].
- Evaluation of the number of cycles for the detection of SARS-CoV-2 viral load by RT-PCR and application of the standard curve for viral load calculation; [Period: until D15, D21 and D28, approximately 14-30 days].

¹⁴ According to the WHO Working Group on Characterization and Clinical Management of COVID-19 Infection (July, 2020), clinical and virological absence of infection (non-detectable RT-PCR) is suggestive of CURE for initially infected participants.

- Analysis of the relationship between the calculated viral load and the clinical progress of participants in the AZVUDINE (FNC) group compared to the control group; [Period: until D15, D21 and D28, approximately 14-30 days].
- Time and proportion of lung imaging improvement during treatment (Pattern of ground-glass opacities, mosaic paving, alveolar consolidation, reticular pattern/septal thickening, opacity with inverted halo, pleural/pericardial effusion,

fibrosis and/or lymphadenomegaly); [Period: until D15, D21 and D28, approximately 14-30 days].

- Time of improvement and proportion of respiratory symptoms and signs during treatment (Lung rales, cough, sputum, sore throat); [Period: until D15, D21, and D28, approximately 14-30 days].
- Time to normalization of ₀₂ saturation (above 95%); [Period: until D15, D21 and D28, approximately 14-30 days].
- Time to normalization of respiratory rate to levels ≤ 24rpm, in room air; [Period: until D15, D21 and D28, approximately 14-30 days]
- Frequency of supplemental oxygenation or non-invasive ventilation; [Period: until D15, D21 and D28, approximately 14-30 days].
- Frequency of invasive mechanical ventilation or extracorporeal membrane oxygenation (ECMO); [Period: until D15, D21, and D28, approximately 14-30 days].
- Proportion of moderate cases that progressed to severe cases requiring intensive care unit (ICU) care; [Period: until D15, D21, and D28, approximately 14-30 days].
- Length of hospital stay; [Period: until D15, D21 and D28, approximately 14-30 days].
- Occurrence of drug interactions; [Period: until D15, D21 and D28, approximately 14-30 days].
- Frequency and intensity of adverse events; [Period: until D15, D21 and D28, approximately 14-30 days].
- Frequency and intensity of unexpected adverse events; [Period: until D15, D21 and D28, approximately 14-30 days].
- Frequency and intensity of serious adverse events; [Period: until D15, D21 and D28, approximately 14-30 days].
- Taxa de mortalidade por todas as causas durante o estudo; [Período: até o D15, D21
 e D28, aproximadamente 14-30 dias]
- Evaluate the tolerability of AZVUDINE (FNC) use at 5mg/day regimen for up to 14 days: [Period: until D15, approximately 14 days].
 - Calculating treatment adherence;

- Total time of use of AZVUDINE (FNC);
- o Proportion of participants who withdrew consent;
- o Proportion of participants who dropped out of treatment.

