8.3. ADVERSE EVENT OF SPECIAL INTEREST

According to the results of the current clinical trials, the adverse events that may be related to the product are:

- Dizziness;
- Headache;
- Decreased phosphorus in the blood;
- Increased alanine aminotransferase;
- Increased aspartate aminotransferase;
- Increased total bilirubin;
- Increased y-glutamyl transferase;
- Decreased neutrophils;
- Increased glucose in the blood.

•

However, according to the AE incidence data reported in the clinical

development phases of the FNC performed earlier, among the AEs already described, AEs of special interest will be considered:

- Changes in markers of liver function ¹⁵:
 - Elevation of AST/TGO above reference values.
 - Elevation of ALT/GTP above reference values.
- Changes in markers of renal function:

Decrease in estimated Glomerular Filtration Rate (eGFR) <30mL/min.

Grade 3 AEs related to dizziness, due to increased risk of falling.

The Principal Investigator should classify the degree of intensity and correlation (cause and effect) between the test drug and the AE of Special Interest, based on the trial protocol and his own medical judgment, and record it in the specific eCRF. The sponsor should be notified within 7 days about the occurrence of AE of Special Interest.

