11.3. METHOD OF STATISTICAL ANALYSIS

All statistical tests will be two-sided tests.

- If the p-value is ≤0.05, it is considered that there is statistical significance in the test (unless otherwise specified).
- The quantitative indices describe the mean value, standard deviation, median, minimum value, maximum value, lower quartile (Q1), upper quartile (Q3) to be calculated, and the rank indices describe the frequency and percentage of cases.
- Comparison of the two groups under general conditions will be analyzed with appropriate methods according to the types of indicators. Student's ttest or Mann-Whitney test will be used to compare the groups for quantitative data. Chi-square test or Fisher's exact test will be used for categorical data.
- The selected cases should be grouped and at the end of the study determine the three analysis data sets (FAS, PPS, SS).
- For the analysis of demographic information and baseline eigenvalues, the mean value, standard deviation, quartiles, minimum value and maximum value should be calculated for numeric variables. For categorical data, frequency and percentage will be calculated.
- For analysis of medication and drug combination adherence one should calculate the percentage of individuals whose medication adherence is at

least 80-100%. An analysis of the classification of the combination of drugs should also be done.

• For analysis of the primary effectiveness indicator:

Primary Goal

To evaluate the **efficacy and safety of** AZVUDINE (FNC) versus placebo in patients infected with moderate to severe stage SARS-COV-2;

Analysis method:

For the efficacy analysis a logistic regression model will be used with the dependent variable "The proportion of participants with clinical improvement [Period: until D15, approximately 14 days]" and independent variables allocation group, AZVUDINE (FNC) or PLACEBO. For the Safety analysis a logistic regression model will be used with the dependent variable "occurrence of serious adverse events" and independent variables allocation group, AZVUDINE (FNC) or PLACEBO. As a support analysis, with exploratory character, both for efficacy and safety, covariate models will be built as well as other variables that present, in the univariate analysis, statistical significance.

Secondary objective

To evaluate the **clinical outcome** between the AZVUDINE (FNC) group versus placebo in patients infected with moderate to severe stage SARS-COV-2;

Analysis method:

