Univariate analysis of the clinical outcome variables and with the group variable.

- For the secondary efficacy indicator analysis, the coronavirus viral load changes compared to baseline should be calculated for the experimental and control groups separately, as well as the value of the difference between the viral load changes compared to baseline for both groups. The ANCOVA model will be used to estimate the impact of treatment on viral load changes adjusting for other study variables such as disease severity, age, weight, and comorbidities, etc.
 - For analysis of the secondary efficacy indicator one should stratify according to the severity of the disease (severe, severe), following the following statistical methods:

PRIMARY ENDPOINT			ANALYSIS METHOD
•	Propo	rtion of participants with clinical status	Teste t de
	impro	vement [Period: until D15,	Student/Teste de
	appro	ximately 14 days].	Mann-Whitney
	0	The criterion for a participant to have	
		an improvement in clinical status is a	
		decrease on the WHO Clinical	
		Improvement Ordinal Scale in at least	
		one category compared to screening	
		(WHO, Jun/2020).	

SEC	CONDARY OUTCOMES	
•	Proportion of participants with a clinical	Pearson's Chi-
	outcome of cure during the study; [Period:	square test
	until D15, D21, and D28, approximately 14-	
	30 days].	

;	inic	al Trial Design	
		o The clinical endpoint of cure is	Student's t-test /
		defined in this protocol as the	Mann-Whitney
		absence of viral RNA in	test
		collected samples and clinical	
		conditions for	
		hospital discharge.	
	•	Time to normalization of body temperature	Student's t-test /
		(below 37.6c, axillary); [Period: until D15,	Mann-Whitney
		D21 and D28, approximately 14-30 days].	test
		Time to improvement of diarrhea,	Student's t-test /
		myalgia, fatigue, malaise, cough and	Mann-Whitney
		headache; [Period: until D15, D21 and	test
		D28, approximately 14-30 days].	
		Changes in liver and kidney function	Student's t-test /
		baselines, and inflammatory and	Mann-Whitney
		immunological markers: [Period: until	test
		D15, D21 and D28, approximately 14-30	
		days]	
		 Lab tests performed on days D1, 	
		D3, D5, D7, D9, D13, D15, D21,	
		D28, and D60.	
		Evaluation of the time to negative	Student's t-test /
		conversion of SARS-CoV-2 viral load by	Mann-Whitney
		RT-PCR between AZVUDINE (FNC) group	test
		and placebo- control group; [Period: until	
		D15, D21 and D28, approximately 14-30	
		days].	

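### Changes in laboratory markers are compared without the baseline value as a covariate: a valid test, but less precise than baseline-adjusted ANCOVA

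*Protocol*

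**What the plan says.** Protocol section 7.1.2 lists as a secondary outcome "Changes in liver and kidney function baselines, and inflammatory and" immunological markers. For quantitative data in general, section 11.3 says that a Student's t-test or Mann-Whitney "test will be used to compare the groups for quantitative data", and its table of secondary outcomes assigns the same pair to this row. For the secondary objective it asks for "Univariate analysis of the clinical outcome variables and with the group variable".

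Two other statements in section 11.3 bear on the point:
- Just before the table, it says that for the secondary efficacy indicator "one should stratify according to the severity of the disease (severe, severe"). The two levels are printed as the same word, and nothing says how a t-test or Mann-Whitney is to be stratified.
- A covariate model is named for one outcome only: "The ANCOVA model will be used to estimate the impact of treatment on viral load changes adjusting for other study variables". The examples listed are severity, age, weight and comorbidities. Baseline viral load is not among them.

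Table 10 schedules these markers on D1, and biochemistry also at D-1. Section 8.3 includes "Changes in markers of liver function" and a fall in eGFR among the events of special interest.

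**The concern.** The baseline value of a laboratory marker usually predicts its later value. A change score removes the baseline by plain subtraction, that is, with a fixed coefficient of 1. When the true regression slope is below 1, this over-corrects. The comparison is then noisier than it need be, and a chance difference between the arms at baseline passes in part into the estimated effect.

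The entry criteria leave room for a wide baseline spread: section 5.2.4 sets the transaminase exclusion at 5 times the normal limit. Section 2.5 reports that adverse reactions in the Chinese phase III study were mainly rises in ALT and AST, mostly grade 1. A sharper comparison of the continuous values would therefore be of some use. At stake is the precision of one group of secondary comparisons, using data that the trial collects anyway.

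**Working it through.** **Inputs.** Two-sided 5% level (section 11.3). 81 evaluable participants per arm (section 11.1, before the 10% allowance that gives 90). The correlation rho between baseline and follow-up is not in the protocol, so I show 0.3 to 0.9. Assumption: the marker has the same variance s² at baseline and follow-up.

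**The plan's own figure.** The protocol states no power, standard deviation or precision for laboratory changes. Its only calculation is for the primary endpoint: (1.645 + 0.842)² × [0.667×0.333 + 0.281×0.719] / (0.386 − 0.205)² = 80.04, hence 81 per arm. This reproduces the stated 80.043 with a one-sided 5% level. It is used here only to fix n.

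**Variances.**
- Change score: 2s²(1−rho).
- ANCOVA on baseline: s²(1−rho²).
- Ratio, ANCOVA to change: (1−rho²) / [2(1−rho)] = (1+rho)/2.

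**Power.** If the t-test on change has 80% power, ANCOVA has Φ((1.960 + 0.842)/√ratio − 1.960). In the other direction, if ANCOVA has 80%, the t-test on change has Φ((1.960 + 0.842)×√ratio − 1.960). Example at rho 0.5: 2.802/√0.75 − 1.960 = 1.275, which gives 90%.

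**Detectable difference** (80% power, in SDs of the marker, 81 per arm): 2.802 × √(2/81) × √[2(1−rho)] for change, and the same with √(1−rho²) for ANCOVA.

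| rho | Variance ratio | ANCOVA power when change has 80% | Change power when ANCOVA has 80% | Detectable difference, change / ANCOVA |
|---|---|---|---|---|
| 0.3 | 0.65 | 94% | 62% | 0.521 / 0.420 |
| 0.5 | 0.75 | 90% | 68% | 0.440 / 0.381 |
| 0.7 | 0.85 | 86% | 73% | 0.341 / 0.314 |
| 0.8 | 0.90 | 84% | 76% | 0.278 / 0.264 |
| 0.9 | 0.95 | 82% | 78% | 0.197 / 0.192 |

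**Simulation check.** With 4,000 runs per setting at 81 per arm and rho 0.3, 0.5 and 0.7, the t-test on change rejected a true null in 4.6 to 5.0% of runs. Under the alternative it had 62, 67 and 73% power, where ANCOVA had 79 to 80%.

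**Baseline imbalance.** The standard error of a baseline difference is √(2/81) = 0.157 SD. A chance imbalance of that size shifts the change-score difference by (1−rho) × 0.157: 0.11, 0.08 and 0.05 SD at rho 0.3, 0.5 and 0.7, and 0.03 and 0.02 SD at 0.8 and 0.9. ANCOVA removes this shift.

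**Schedule check.** As Table 10 reads, the biochemistry and inflammatory markers have a D15 column entry. The immunological markers appear at D1, D21 and D28 only. Note 5 restricts D21 to participants still in hospital. Note 2 moves the D15 examinations forward when treatment stops early.

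**The case against.** The strongest reply is that nothing here is an error. Under randomisation a t-test on change keeps its level, as the simulation confirms, and chance imbalance is already covered by the stated error rate. The baseline is not ignored, because it enters by subtraction. Section 11.3 also asks for stratification by severity, so the comparison is not wholly unadjusted. All of this stands, and it confines the point to precision.

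A reader might infer that this is the endpoint that would reveal liver harm. The documents do not support that. Section 8.3 makes ALT/AST elevation and low eGFR events of special interest, and section 11.3 separately lists counts and rates of laboratory values becoming abnormal or worsening. Individual elevations show better there than in group means, and ANCOVA does not change that. The earlier rises were mainly grade 1, and section 8.3 says only that such events may be related to the drug.

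Three further limits stand:
- The viral-load ANCOVA is a precedent for covariate modelling, but not clearly for baseline adjustment.
- Lack of stratification in the randomisation cannot be claimed, because section 5.4.1 refers to Annex 2, which is not shown.
- The calculation compares ANCOVA with the t-test only. The gain over Mann-Whitney on change was not computed.

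It may also be said that covariates belong in the statistical analysis plan. Here, though, the protocol does not leave the method open. It names tests for this row.

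**Conclusion.** The point holds as a minor matter of efficiency. The tests named for the laboratory-marker row omit the baseline covariate and so give up precision that is available from data already scheduled. The loss is a fraction (1−rho)/2 of the sample: 35% at rho 0.3, 15% at 0.7 and 5% at 0.9. In power, 80% on change corresponds to between 94% and 82% with ANCOVA over that range. A reader who stopped at rho 0.7 might infer a gain of at least 5 points, but at 0.8 and 0.9 it is about 4 and 2.

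The figures rest on equal variances at the two times and on an assumed rho, and the 80% starting power is illustrative. A reader might also infer bias or an inflated type I error from the missing covariate. Neither follows.

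**What to change.** In the laboratory-marker row of the section 11.3 table:
- Make the main analysis an ANCOVA of the post-baseline value on allocation, the last pre-dose value of the same marker, and disease severity. Correct the duplicated severity levels. State that the D1 sample counts as baseline only if drawn before the first dose; dosing at 8 pm makes this feasible.
- Log-transform skewed markers (ALT, AST, GGT, bilirubin, CRP, IL-6, procalcitonin) and report geometric-mean ratios with 95% confidence intervals.
- For markers scheduled then, use the end-of-treatment visit: D15, or the early-termination visit. Acknowledge that its timing varies between participants.
- For immunological markers use D28. Before relying on it, reconcile Table 10, which marks these tests at D28, with its note 3, which leaves D28 examinations to the Principal Investigator, and with the visit 19 list in section 7.3, which shows no blood sample.
- Label D21 results as descriptive, because only participants still in hospital are measured.
- Keep the t-test / Mann-Whitney as supportive.

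The cost is analysis wording, plus the D28 reconciliation. No extra participants are needed. The small downside is that skewed markers are reported as ratios and not as raw differences.
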